**Table 6: Probability of Meeting Safety Review Trigger Under Potential Rates of True Toxicity (N=6)**

True Toxicity Rates		Probability of Meeting Safety Review Trigger
Grade $\geq$ 3 adverse events at least possibly related to the VRC01, VRC01LS, or VRC07-523LS immunization, excluding Grade 4 events probably or definitely attributable to the study immunization	Life-Threatening adverse event or Grade 4 events probably or definitely attributable to the VRC01, VRC01LS or VRC07-523LS immunization	
.50	.00	.89
.50	.05	.94
.50	.25	1.00
.25	.00	.47
.25	.05	.63
.25	.25	.83
.05	.00	.03
.05	.05	.29
.05	.25	.83
.00	.05	.26
.00	.25	.82

For example, Table 6 shows that there is a 94% chance of failing the safety guidelines under conditions in which the true rate of life-threatening toxicity is 5% and the rate of non-life-threatening toxicity is 50%. Assuming that a dosing regimen associated with this extent of severe toxicity would be unacceptable, the 6% chance of passing the safety criteria under these conditions would represent sampling error. Note that the true rate of Grade 3 events would have to be quite high to provide a strong probability of pausing the study at a dose where there is no life-threatening toxicity and no Grade 4 events at least probably attributable to VRC01, VRC01LS, or VRC07-523LS. This is considered acceptable, since a larger sample size would be needed to increase the probability of pausing the study at lower rates of Grade 3 events, and this would entail exposing greater numbers of children to an experimental dose, which may be either toxic or subtherapeutic.

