## 8.4 Sample Size and Accrual

Both mothers and infants are enrolled in the study, but only infants receive the VRC01, VRC01LS, or VRC07-523LS immunization(s) and are followed on the study. The study will enroll 79 mother-infant pairs: 13 in each of Dose Groups 1-3 and 10 in each cohort in Dose Groups 4 and 5, with the aim of having 10 evaluable infants in each Dose Group 1-3 and 8 in each cohort in Dose Groups 4 and 5. Evaluable infants must have received the required study immunization(s) and have completed follow-up for the primary safety outcome measure (Day 28 evaluations for Dose Groups 1, 2 and Cohort 1 from Dose Groups 4 and 5; Week 24 evaluations for Dose Group 3; and Week 16 evaluations for Cohort 2 in Dose Groups 4 and 5). This assumes a maximum missing data rate of 23% in Dose Groups 1-3 and 20% in Dose Groups 4 and 5. Non-evaluability could be due to losses to follow-up, missed visits or problems with laboratory samples. Note that infants who do not receive the first immunization will be replaced.

Safety data will be assessed as described in Section 8.5.1. If any of the safety criteria are triggered, enrollment and further immunizations will be temporarily stopped until the SMC reviews the data and advises the protocol team on how to proceed. Section 8.5.1 discusses the error probabilities associated with the safety criteria and Section 8.6.1.2 discusses the precision that the sample size will provide for estimating AE rates and PK success rates. The sample size is based on target precision for the estimation of key safety and PK parameters. The calculations are located in Section 8.6.1.2 for ease of discussion.

We had anticipated that all participants in Dose Groups 1 and 2 would be enrolled within 2 years after Version 1.0 was opened to accrual. In fact, enrollment into both dose groups was more rapid than anticipated: taking less than 9 months to reach full accrual of each dose group. Likewise, Dose Group 3 reached full accrual within approximately 4 months. We had anticipated that Dose Group 4 would be fully enrolled within 1 year of that dose group being opened to accrual. However, this group also reached full accrual much faster than expected, within 6 months. It is anticipated that both cohorts in Dose Group 5 will be enrolled within 1 year after Version 4.0 opens to accrual.

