### 8.5.1 Stopping Rules for Safety

Stopping rules have been and will be applied in order to protect the study participants from unnecessary exposure to the monoclonal antibody, should the safety profile prove unacceptable in this population. The evaluation of safety for the purpose of applying these guidelines will be based on data:

- through the first 28 days after immunization for Dose Groups 1, 2, and Cohort 1 of Dose Groups 4 and 5;
- on data through the first 8 weeks after the first immunization for Dose Group 3, which reflects the time point when this group would have received more immunizations than Dose Groups 1 and 2;
- on data through the first 28 days after the second immunization in Dose Groups 4 and 5, Cohort 2 (Week 16).

Due to the fact that infant hyperbilirubinemia is common in the first four to five weeks of life, especially during breastfeeding, and that Grade 3 neutropenia and anemia are common in infants on ARVs, these toxicities will not be counted in the safety evaluation algorithm presented below.

NOTE: If at any time during the study the triggers below are met, the study will be paused for evaluation, as described below and an SMC review performed within 7 days. The SMC will decide what additional data they would like to see and advise the study team on how to proceed.

To assess the early safety of the initial doses of VRC01, VRC01LS, and VRC07-523LS monoclonal antibodies, data from the first 6 infants immunized and followed through day 28 in Dose Groups 1, 2, and Cohort 1 of Dose Groups 4 and 5 will be examined.

Similarly, the early safety of the multiple dose regimen of VRC01 monoclonal antibody in Dose Group 3 will be assessed based on data from the first 6 infants immunized and followed through Week 8. The early safety of the multiple-dose regimen of VRC01LS in Dose Group 4 (Cohort 2) and of VRC07-523LS in Dose Group 5 (Cohort 2) will be assessed based on data from the first 6 infants who have reached 28 days after the second dose (Week 16).

- If any of the infants dies or has a life-threatening adverse event or any Grade 4 event that is possibly, probably or definitely attributable to the VRC01, VRC01LS, or VRC07-523LS immunization, or
- If two or more of the six infants have a Grade  $\geq 3$  adverse event at least possibly related to the VRC01, VRC01LS, or VRC07-523LS immunization (excluding Grade 3 neutropenia and anemia, and hyperbilirubinemia), then future enrollment and immunizations will be stopped.

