The extent to which the safety guidelines protect against the errors described above can be assessed by examining various hypothetical rates of "true toxicity" which could occur, if the study medication were used extensively among the participant population at the dose levels under question. The hypothetical situations presented in Table 6 range from conditions under which a given dosing regimen would cause a high incidence of severe and life-threatening adverse events to conditions under which severe adverse events would be relatively rare and would not be life-threatening. For each of these hypothetical situations, we assume that a sample of six participants is drawn from the participant population and that the safety guidelines, summarized above, are followed.

Please note that the probabilities presented below would not apply if data from more than six infants were used.

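### Table 6 gives a trigger probability of .83 for true rates of .25 and .25, but the calculation that produces its other ten entries gives .94

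*Protocol*

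**What the plan says.** Section 8.5.1 of the protocol sets two conditions for the early review of the first six infants in a group. The first is met by one infant: "If any of the infants dies or has a life-threatening adverse event or any Grade 4 event that is possibly, probably or definitely attributable" (meaning caused by the study antibody). The second begins "If two or more of the six infants have a Grade" and sets the threshold at Grade 3 or higher, at least possibly related, with listed exclusions. If either condition is met, enrolment and immunization stop and the Study Monitoring Committee is consulted.

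The section then evaluates the rule under hypothetical true toxicity rates: "we assume that a sample of six participants is drawn from the participant population". Table 6, titled "Probability of Meeting Safety Review Trigger Under Potential Rates of True Toxicity (N=6", gives the results for eleven pairs of rates. The heading of its first column adds "excluding Grade 4 events probably or definitely attributable to the study immunization", so an infant counted in the second column (life-threatening or attributable Grade 4 events) is not also counted in the first.

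The sixth row (.25 and .25) prints .83. The ninth row (.05 and .25) also prints .83. The text below the table works through one case, true rates of .50 and .05: "Table 6 shows that there is a 94% chance of failing the safety guidelines" there, leaving a 6% chance of passing. Section 8.4 sends the reader to this material: "Section 8.5.1 discusses the error probabilities associated with the safety criteria".

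**The concern.** The two rows printed as .83 differ only in the first rate, which is .05 in one and .25 in the other. A fivefold rise in related Grade 3 or higher events should raise the chance of triggering, and elsewhere in the table it does. The same step takes the probability from .03 to .47 when the second rate is 0, and from .29 to .63 when it is .05. At a second rate of .25 the printed column runs .82, .83, .83, 1.00 as the first rate goes through 0, .05, .25 and .50.

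Table 6 is where the protocol quantifies the chance that the rule lets a toxic regimen through, in a study of newborns. A committee member or ethics reviewer who uses the sixth row would take that chance to be 17% when it is about 6%.

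**Working it through.** **Inputs**
- n = 6 infants (Section 8.5.1, text before Table 6).
- p = true rate in the first column, q = true rate in the second column.
- The categories are mutually exclusive (Table 6, first column heading).
- The rule triggers with at least one q event, or at least two p events among the six (Section 8.5.1).

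**Formula.** The protocol does not print one. From the inputs above, and with infants independent of each other, the rule is not triggered only when there are no q events and no more than one p event:

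P(trigger) = 1 − [(1 − p − q)^6 + 6p(1 − p − q)^5]

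**Reproducing the protocol's worked example** (p = .50, q = .05, so 1 − p − q = .45):

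.45^6 = .0083 and 6 × .50 × .45^5 = .0554. P(trigger) = 1 − .0637 = .936, printed as .94. It agrees.

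**All eleven rows**

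| p | q | Computed | Printed |
|---|---|---|---|
| .50 | .00 | .8906 | .89 |
| .50 | .05 | .9363 | .94 |
| .50 | .25 | .9968 | 1.00 |
| .25 | .00 | .4661 | .47 |
| .25 | .05 | .6302 | .63 |
| **.25** | **.25** | **.9375** | **.83** |
| .05 | .00 | .0328 | .03 |
| .05 | .05 | .2914 | .29 |
| .05 | .25 | .8319 | .83 |
| .00 | .05 | .2649 | .26 |
| .00 | .25 | .8220 | .82 |

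Ten rows agree to two decimals. One does not.

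**The disputed row by hand** (p = .25, q = .25, so 1 − p − q = .50):

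.50^6 = .0156 and 6 × .25 × .50^5 = .0469. The sum, the chance of passing, is .0625. P(trigger) = 1 − .0625 = .9375.

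**Could another reading give .83?**
- The two event types independent, 1 − (1 − q)^6 × P(Bin(6, p) ≤ 1): .905 for this row. It also gives .920 for the row printed as .94.
- p taken to include q: .822, which rounds to .82. It also gives .90 where .94 is printed and .54 where .63 is printed.
- First condition alone, 1 − (1 − q)^6: .822 here, but 0 for the row printed as .89.
- Second condition alone: .466.
- Sum of the two separate trigger probabilities, capped at 1: 1.00.

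None of these gives .83 in this row, and none fits the rest of the table.

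**Size of the error.** The implied chance of passing is 1 − .83 = .17. The computed chance is .0625. The ratio is .17 / .0625 = 2.7.

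**The case against.** The arithmetic is not open to dispute, but its importance is. Four points deserve weight.

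- **The error is on the cautious side.** The printed value understates the protection, so nobody relying on it would be falsely reassured. This stands.
- **Nothing else uses the entry.** The trigger conditions, the six-infant review, the sample size and the analyses do not depend on it. The worked example and the closing remark about Grade 3 events without life-threatening toxicity rest on other rows, which are correct. This also stands.
- **The table is illustrative.** The protocol calls its scenarios hypothetical and says the probabilities do not apply once data from more than six infants are used. Section 8.1 reports a ten-infant review for Dose Group 1, and Section 8.5.1 adds a continuing pause at a rate above 30%. All true, but the section offers the table as the measure of how well the rule guards against error, so its entries should be right.
- **The table's categories are not quite those of the rule.** The second column counts Grade 4 events that are probably or definitely attributable, while the rule also triggers on one that is only possibly attributable. So .94 is the right entry under the table's own definitions, and not necessarily the exact probability for the rule as written. Since the rule triggers on a single such event, it would trigger at least as often as the table's categories indicate.

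The repeated .83 is not proof by itself, because rounding to two decimals can hide a small rise. The recalculation is the proof.

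**Conclusion.** The .83 in the sixth row of Table 6 is an isolated numerical error; the entry should be .94 (.9375). The chance of passing a regimen with these rates is about 6%, against an implied 17%. The conclusion rests on the six-infant sample, independent infants and the mutually exclusive categories in the table headings, and the agreement of the other ten rows supports that reading. A value carried over from the .05 and .25 row would explain the error, but the documents do not show its cause. The consequence is confined to a misstated operating characteristic of the safety rule, in the conservative direction.

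**What to change.** In Protocol Section 8.5.1, Table 6, row with true rates .25 and .25, replace .83 with .94. No rule, sample size, analysis or other entry needs to change.

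The edit is one number; the cost lies in the route. A letter of amendment goes to every site's ethics committee for approval and needs a registration packet, which is heavy for one table entry. The study has already used a clarification memorandum for which the sponsor did not require prior ethics committee approval. If the sponsor considers that route suitable here, it would be lighter; otherwise the correction can go into the next amendment.

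### Protocol Table 6 prints .83 for the .25/.25 row where the table's own model gives .94, and its labels set a higher attribution level for Grade 4 events than the stopping rule does

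*Protocol*

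**What the plan says.** Protocol Section 8.5.1 sets two triggers for the first six infants evaluated in a group or cohort. One infant is enough if the infant dies, has a life-threatening event, or has "any Grade 4 event that is possibly, probably or definitely attributable to the VRC01, VRC01LS, or VRC07-523LS immunization". Otherwise two or more of the six must have an event of Grade 3 or higher that is at least possibly related.

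Section 8.4 refers the reader to Section 8.5.1 for the error probabilities of these criteria, and Table 6, titled "Probability of Meeting Safety Review Trigger Under Potential Rates of True Toxicity (N=6", supplies them. Its first column is the rate of related events of Grade 3 or higher, "excluding Grade 4 events probably or definitely attributable to the study immunization". Its second column is headed "Life-Threatening adverse event or Grade 4 events probably or definitely attributable to the VRC01, VRC01LS or VRC07-523LS immunization". With .25 in both columns the printed trigger probability is .83.

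The text below the table works through the row .50/.05: a 94% chance of triggering, so that "the 6% chance of passing the safety criteria under these conditions would represent sampling error". It then comments on a dose with "no life-threatening toxicity and no Grade 4 events at least probably attributable to VRC01, VRC01LS, or VRC07-523LS", noting that Grade 3 rates would have to be quite high to pause the study there.

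**The concern.** With column 2 held at .25, the printed probabilities for column 1 rates of .00, .05, .25 and .50 are .82, .83, .83 and 1.00. More column 1 toxicity must raise the chance of triggering, so a flat step from .05 to .25 followed by a jump to 1.00 is implausible. As printed, a regimen with 25% toxicity in each column would seem to pass 17% of the time (1 − .83), nearly three times the 6% that the protocol's worked example treats as sampling error.

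The attribution wording also differs. The rule stops on a single possibly attributable Grade 4 event. The two headings and the sentence after the table start at probable attribution. Read literally, a possibly related Grade 4 event that is not life-threatening would fall in column 1, where two infants are needed.

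At stake is the accuracy of the protocol's only tabulation of how this rule performs, in a Phase 1 study of newborns.

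**Working it through.** **Inputs.** n = 6 (the sampling assumption stated before Table 6). The trigger is one column 2 infant or at least two column 1 infants (Section 8.5.1). p1 and p2 are the column 1 and column 2 rates. The exclusion in the column 1 heading separates the Grade 4 categories; I take the columns as fully exclusive, so each infant counts in at most one.

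**Formula.** The rule is passed if no infant has an event in either column, or if exactly one has a column 1 event and the other five have none:

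P(trigger) = 1 − [(1 − p1 − p2)^6 + 6·p1·(1 − p1 − p2)^5]

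**The plan's worked example first** (.50/.05): 1 − p1 − p2 = .45. Then .45^6 = .0083 and 6(.50)(.45^5) = .0554, which sum to .0637. P = .9363, printed .94. The chance of passing is 6.37%, in line with the stated 6%.

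**All eleven rows:**

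| p1 | p2 | Printed | Computed |
|---|---|---|---|
| .50 | .00 | .89 | .8906 |
| .50 | .05 | .94 | .9363 |
| .50 | .25 | 1.00 | .9968 |
| .25 | .00 | .47 | .4661 |
| .25 | .05 | .63 | .6302 |
| **.25** | **.25** | **.83** | **.9375** |
| .05 | .00 | .03 | .0328 |
| .05 | .05 | .29 | .2914 |
| .05 | .25 | .83 | .8319 |
| .00 | .05 | .26 | .2649 |
| .00 | .25 | .82 | .8220 |

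Ten rows agree to two decimals. The row that fails is 1 − [.5^6 + 6(.25)(.5^5)] = 1 − [.015625 + .046875] = 1 − .0625 = .9375. With p2 = .25, the formula rounds to .83 only for p1 between about .03 and .06.

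**Could another model give .83?**

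- Independent columns, 1 − (1 − p2)^6·[(1 − p1)^6 + 6·p1·(1 − p1)^5]: .905 for this row. It also misses .50/.05 (.9196 against .94), .50/.25 (.9805 against 1.00) and .25/.05 (.6075 against .63), so it matches 7 of 11 rows.
- Column 1 rate conditional on no column 2 event: .905.
- Two or more of six at the combined rate p1 + p2: .891.
- Column 1 including column 2: .822 for this row, but .90 for .50/.05 (printed .94).
- Column 2 events only: .822 for this row, but .26 for .50/.05 (printed .94).

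None rounds to .83.

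**The attribution wording.** The formula depends only on the two rates, so renaming the columns leaves every computed value as it is. A numerical effect appears only if some share f of the events counted in column 1 are possibly related Grade 4 events that are not life-threatening, since the actual rule treats these as column 2 events. The documents do not give f. As an assumption only, replacing p1 by (1 − f)p1 and p2 by p2 + f·p1 gives:

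| Row | f = 0 | f = .05 | f = .10 | f = .20 |
|---|---|---|---|---|
| .05/.00 | .03 | .04 | .06 | .08 |
| .25/.00 | .47 | .48 | .50 | .54 |
| .05/.05 | .29 | .30 | .31 | .33 |

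**The case against.** The strongest reply is that this is an erratum with no consequence. The rule acts on observed counts and never consults Table 6. The worked example is right. The passage that accepts low power against Grade 3 events rests on rows with no column 2 toxicity, and those rows reproduce. The faulty row describes a regimen far more toxic than Section 8.1 anticipates. Dose Groups 1 to 4 are fully enrolled, and the Letter of Amendment describes Dose Group 5 Cohort 2 as completing its dosing, so by inference few if any six-infant reviews remained. All of this stands, and it keeps the severity low. It does not make .83 correct.

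On the wording, it is fair to say that the table's author probably meant column 1 as Grade 3 toxicity. The worked example contrasts the columns as "the true rate of life-threatening toxicity is 5% and the rate of non-life-threatening toxicity is 50" per cent, and the closing comment speaks of Grade 3 events. That points to f near zero. This also stands, which is why the wording comes second to the wrong figure.

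Two stronger readings are tempting. A reader might infer that infants are less protected than the protocol claims. The documents show the reverse: the true trigger probability is higher than printed, and the operative rule takes the broader, possible-attribution threshold. A reader might also infer that the wording makes the other printed probabilities wrong. It does not, because each is conditional on the two stated rates and ten of the eleven are computed correctly from them.

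**Conclusion.** The .25/.25 entry is wrong: .83 should be .94 (.9375), an understatement of about 11 percentage points (.9375 − .83 = .1075). The chance of passing is 6.25% rather than 17%, practically the same as the 6.37% of the worked example. This rests on exclusive categories and n = 6, a model confirmed by its match to the other ten rows. The repeat of the .05/.25 value suggests a copying slip, but that is inference.

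The attribution mismatch between the trigger and Table 6 is real but secondary. It is a labelling inconsistency with no documented size; the figures for f above are illustrations.

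Both slips understate protection. No trigger, dose step, endpoint, sample size or analysis depends on either, so this is a low-severity correction of a wrong stated figure.

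**What to change.** In Table 6, change the .25/.25 entry from .83 to .94. In both column headings, extend the attribution wording for Grade 4 events to *possibly, probably or definitely*, so that column 1 becomes Grade 3 events at least possibly related. In the sentence after the table, change *probably* to *possibly*. Leave the Section 8.5.1 trigger and the other ten values as they are.

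Do not use the edit to add a note extending the hyperbilirubinemia, neutropenia and anemia exclusions to column 2. Section 8.5.1 is ambiguous there. A general sentence says "these toxicities will not be counted in the safety evaluation algorithm presented below", but the exclusion is repeated only in the two-infant trigger, and the one-infant trigger carries none. A table note should not settle that in the less protective direction.

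The cost is one number, two headings and one word. The sponsor can choose the vehicle. Clarification Memorandum #1 did not need prior ethics approval, but it was issued for urgent COVID-19 reasons and is weak precedent; the Letter of Amendment did need approval.

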### 8.5.2 Accrual Rate Evaluation

Accrual to this study will be monitored by the IMPAACT leadership in accordance with standard operating procedures. The team will monitor feasibility quarterly, first based on site registration and then on accrual. Initially, the team will monitor site registration quarterly to ensure that an adequate number of sites have registered to complete the protocol. If less than one-third of eligible sites have registered after the protocol has been approved for 6 months, the team will re-assess the feasibility of the protocol and the reasons why sites have not registered and may amend the protocol accordingly. Once one third of eligible sites have registered, the team will assess accrual on a quarterly

basis. If the protocol has not accrued half its participants within 6 months of opening, the team will identify problems in accrual and possibly amend the protocol accordingly.

A full monitoring plan was developed before the study opened to accrual.

